STUDY PROTOCOL

Treatment outcomes of partial pulpotomy using two different calcium silicate materials in cariously exposed mature permanent teeth: A randomized clinical trial

NCT number: has not been created yet

Date of creation: 05.12.2023

In this clinical trial, patients will be blinded; they will not be aware of the material used. Both the clinicians conducting the clinical and radiographic evaluations and the statistician analyzing the data will be blinded to the materials used. Due to the different application procedures of the two materials used, it is not possible for the clinician administering the treatment to be blinded.

After the necessary clinical examination, volunteers meeting the inclusion criteria will be randomized into two groups (n=30 each) by an independent clinician using a randomization table, and this information will be documented in patient cards. All volunteers will receive standard oral hygiene training prior to treatment. The two different calcium silicate-based materials (Biodentine or TheraCal PT) will be applied according to the manufacturers' recommendations and as outlined in their usage instructions. All treatments will be performed by a single endodontist using dental magnification.

The treatment procedure for both groups after the removal of decay and partial removal of the exposed pulp is identical and outlined below:

Prior to treatment, a periapical radiograph of the relevant tooth will be taken for diagnostic purposes using a parallel technique facilitated by a radiograph holder. The process will involve the patient biting on a small amount of silicone placed in the bite block of the radiograph holder to ensure standardization and quality. This same silicone impression will be disinfected and stored under appropriate conditions in the patient's file to be used for subsequent radiographs to ensure consistency of the angles (the filled part of the tooth will be adjusted in the silicone to fit post-filling). Additionally, high-quality images of the relevant teeth will be taken before, during, and after the treatment using a camera. Deep local anesthesia will be achieved using lidocaine with 1/80,000 epinephrine. A rubber dam will be placed to isolate the tooth and eliminate contact with the oral environment. Initial decay removal will be conducted peripherally using a sterile, high-speed diamond bur. Deeper layers of decay will be removed using a series of sterile, low-speed burs of varying diameters. Once the decay is fully removed and the pulp tissue exposed, the initial partial removal of the pulp tissue will be performed using a new sterile high-speed bur. After examining the area for residual decay, a 5.25% NaOCl solution will be used to irrigate the cavity for the initial removal of carious dentin shavings and disinfection of the tissue and cavity. For hemorrhage control, a moist cotton pellet soaked in NaOCl will be placed on the pulp wound surface for 2 minutes. If bleeding continues, a new sterile cotton pellet soaked in 5.25% NaOCl solution will be placed for another 2 minutes. If bleeding persists

after the removal of the new cotton pellet, a second partial pulpotomy will be performed to reach non-inflamed pulp tissue, and the previous procedure will be repeated. Bleeding will be checked every 2 minutes up to 10 minutes; if it stops at any of these intervals, pulp capping will be performed. If bleeding continues for more than 10 minutes, the case will be deemed unsuitable for continuation with the current treatment, and total pulpotomy or root canal therapy will be considered. Once hemostasis is achieved, the pulp capping material (Biodentine or TheraCal PT) will be placed (detailed descriptions of these steps are provided below). Subsequently, the tooth will be restored with permanent composite material, and photographs of the filling will be taken along with a periapical radiograph using the silicone impression. Post-treatment routine advice and postoperative pain information will be provided to the patient, and they will be asked to fill out the postoperative pain scale for the first week after treatment and note any medications and dosages used if applicable. Follow-up visits at 1 week (for pain assessment only) and at 3, 6, and 12 months will be conducted. During these follow-ups, necessary clinical examinations (percussion, palpation, presence-absence of sinus tract) will be performed, vitalometric assessments recorded, radiographs taken using the silicone impression, and evaluations of lamina dura, presence of lesions, and canal obliteration conducted, along with scoring of filling quality. If issues such as pain, swelling, sinus tract formation, or lesion development are detected during follow-up, root canal treatment will be administered, and the case will be deemed a failure. Radiographic follow-up evaluations of the patients will be independently performed by two endodontists not involved in the study.

Biodentine Group: After mixing the Biodentine material according to the guidelines provided in the application manual, it will be placed vertically over the hemostatically treated pulp using a carrier to ensure no exposed pulp remains. After a setting time of 12 minutes, a self-etch bond will be applied around the material, thinned with air, and light-cured. Flowable composite will then be placed over the Biodentine material and light-cured. Next, selective etching of the enamel will be performed in the cavity, washed off with water, dried, then self-etch bond applied and light-cured, followed by layering of the composite filling. If possible, filling procedures will also be performed under the rubber dam. If issues arise with matrix placement under the rubber dam, the Biodentine surface will be completely covered with flowable composite and light-cured; subsequently, the rubber dam will be removed, and filling will continue.

TheraCal PT Group: TheraCal PT material will be placed over the hemostatically treated pulp using the injector tip found in its package to ensure no exposed pulp remains, and light-cured for 10 seconds. Subsequently, self-etch bond will be applied over and around the material, thinned with air, and light-cured. Flowable composite will then be placed over the TheraCal PT and light-cured. Remaining procedures are identical to those for the Biodentine group.

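### The arm is allocated before haemostasis is judged, and nothing stated keeps it from the unblinded operator until capping, where the arms first differ

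*Protocol*

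**What the plan says.** The protocol is unnumbered, so places are given by topic.

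- **Randomisation (opening section).** "After the necessary clinical examination, volunteers meeting the inclusion criteria will be randomized into two groups (n=30 each) by an independent clinician". The same sentence goes on to name the tool and the place where the arm is recorded: "using a randomization table, and this information will be documented in patient cards".
- **Operator (opening section).** "All treatments will be performed by a single endodontist using dental magnification". On blinding: "Due to the different application procedures of the two materials used, it is not possible for the clinician administering the treatment to be blinded".
- **Treatment procedure, exposure.** "Once the decay is fully removed and the pulp tissue exposed, the initial partial removal of the pulp tissue will be performed".
- **Treatment procedure, haemostasis.** "Bleeding will be checked every 2 minutes up to 10 minutes; if it stops at any of these intervals, pulp capping will be performed". And: "If bleeding continues for more than 10 minutes, the case will be deemed unsuitable for continuation with the current treatment". If bleeding persists after the second cotton pellet, a second partial pulpotomy is done to reach tissue that is not inflamed.
- **Biodentine Group and TheraCal PT Group.** Both descriptions start with the material going onto a pulp where bleeding has already been controlled. Biodentine then sets for 12 minutes; TheraCal PT is light-cured for 10 seconds.

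The protocol does not mention sealed envelopes, concealment of the next assignment, or withholding the arm from the operator until a given step.

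**The concern.** As the text is ordered, a volunteer has an arm before the operator knows whether the pulp will be exposed and whether bleeding will stop. Reading the bleeding at each check decides which randomised teeth leave the study treatment. That reading is a judgement made by one person who is declared unblinded.

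The reason given for not blinding the operator is that the two materials are applied differently. This is true only from capping onward, so it does not justify knowledge of the arm during the earlier decisions.

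The protocol itself links persistent bleeding to inflamed tissue. If exits depended on the arm, the capped groups could differ in prognosis for a reason other than the material. The handling contrast (12 minutes v 10 seconds) is a practical difference that an operator who knows the arm would face. The protocol states no preference for either material, and nothing shows that this contrast would change a bleeding check. The risk is one of opportunity, not of demonstrated behaviour.

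**Working it through.** **Step 1: order of events.**

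| Step | Where stated | Depends on the arm? |
|---|---|---|
| Clinical examination, inclusion, randomisation, card entry | Opening section | Arm is set here |
| Decay removal, exposure, first partial pulpotomy | Treatment procedure | No |
| Bleeding checks, possible second pulpotomy, exit beyond 10 minutes | Treatment procedure | No |
| Placement of capping material | Treatment procedure; the two group descriptions | Yes, first difference |

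Everything in the second and third rows can be done without knowing the arm.

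**Step 2: the plan's own figure.** The only relevant figure is 30 per arm. It cannot be reproduced, because this document gives no success rate, effect size, error rate or power. It is used below only as an input.

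**Step 3: possible bias if exits are left out of the analysis.** All rates are assumptions. Let d be the share of teeth slow to stop bleeding, s_d their success if capped, and q the fraction of slow teeth that exit. Overall success if all teeth were capped is 85% in both arms, so success in the remaining teeth is s_r = (0.85 − d·s_d)/(1 − d). Then

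success among capped = [s_r(1 − d) + s_d·d(1 − q)] / [(1 − d) + d(1 − q)].

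With equal q in both arms the difference is 0. Otherwise, in percentage points:

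| Case | s_r | q = 0.40 v 0.60 | q = 0.25 v 0.75 | q = 0 v 1 (limit) |
|---|---|---|---|---|
| d = 0.05, s_d = 0.7 | 0.8579 | 0.16 | 0.39 | 0.79 |
| d = 0.10, s_d = 0.5 | 0.8889 | 0.78 | 1.94 | 3.89 |
| d = 0.20, s_d = 0.5 | 0.9375 | 1.73 | 4.33 | 8.75 |

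Worked example, last row, 0.25 v 0.75: (0.75 + 0.10 × 0.75)/(0.80 + 0.20 × 0.75) = 0.825/0.95 = 86.84%; (0.75 + 0.10 × 0.25)/(0.80 + 0.20 × 0.25) = 0.775/0.85 = 91.18%; difference 4.33 points. The arm with more exits looks better.

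**Step 4: possible bias if exits are counted as failures.** The difference is d × s_d × (difference in q), and its direction reverses. At 40% v 60% it runs from 0.05 × 0.5 × 0.2 = 0.5 points to 0.20 × 0.7 × 0.2 = 2.8 points. At 25% v 75% it runs from 0.05 × 0.5 × 0.5 = 1.25 points to 0.20 × 0.7 × 0.5 = 7 points. Neither way of handling exits in the analysis removes the problem.

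**Step 5: scale.** Standard error of the difference with 30 per arm at 85%: √(2 × 0.85 × 0.15/30) = 0.0922, or 9.2 points. Every value in Step 3, and every value shown in Step 4, lies below it.

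**The case against.** The strongest reply has four parts.

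1. **The order is inferred.** The inclusion criteria are not in this document, and the title speaks of cariously exposed teeth, so exposure might be checked before randomisation. The sentence "All volunteers will receive standard oral hygiene training prior to treatment" does not place randomisation before training. It is true that the order comes from the sequence of the text. But the text ties randomisation to the clinical examination and describes treatment afterwards, and nothing in it supports a check after exposure or haemostasis.
2. **Silence is not proof.** The protocol does not say when the card is written or whether the operator sees it before capping. This stands, and it limits the claim to what the plan permits. If the arm is already withheld in practice, one sentence settles the matter.
3. **Discretion is narrow.** An independent clinician randomises, the check times are fixed and the same in both arms, and the outcome evaluators and statistician are blinded. These are real safeguards. They do not cover the reading of bleeding itself, and an independent randomiser does not stop the operator from learning the result.
4. **The bias is small and assumed.** With 30 per arm, 5 to 20% slow bleeders is about 1.5 to 6 teeth, and the more plausible values are well below the standard error. This also stands. But such a bias is systematic, the confidence interval does not reflect it, and with so few teeth a difference in exits would be hard to establish. Exits by arm can at least be counted.

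**Conclusion.** The concern holds and should be fixed; confidence is medium. The plan states a point of randomisation, and following it allows an operator who knows the arm to decide which randomised teeth leave before either material is used. The plan's own reason for an unblinded operator does not reach back to that stage.

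No harm is demonstrated, and the size depends wholly on assumed rates. With equal exits there is no bias. With moderately to strongly unequal exits left out of the analysis it is about 0.2 to 4.3 points, and at the extreme limit 0.8 to 8.8 points. The case for change rests on a risk that is avoidable at little cost, not on a large expected error. An analysis plan cannot repair it, because who knew the arm at the chairside is a matter of trial conduct.

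**What to change.** Amend the randomisation paragraph in one of two ways. Neither changes the clinical haemostasis rule or adds a procedure for patients.

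**Preferred: allocate late.** Suggested wording:

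> The independent clinician randomises each volunteer during treatment, for example by opening a sealed envelope, once pulp exposure is confirmed and haemostasis is achieved under the existing rule, immediately before the capping material is placed. Volunteers who do not reach this point are logged as not randomised.

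This removes both the early knowledge and the exits between randomisation and capping. Its cost is that more treatments are started than capped: for 60 capped, 60/0.95 = 63.2, 60/0.90 = 66.7 or 60/0.80 = 75.0 starts if 5%, 10% or 20% exit (assumed), so about 63, 67 or 75. Conclusions then apply to teeth that reach haemostasis.

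**Alternative: disclose late.** Keep randomisation where it is and add:

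> The arm is withheld from the operator, and from any record the operator can see, until immediately before the capping material is placed. All randomised volunteers stay accounted for in their assigned group.

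This needs no extra starts and does not change the population. It removes the early knowledge only. Exits after randomisation remain: at the same assumed rates, 30 × 0.95 = 28.5, 30 × 0.90 = 27 or 30 × 0.80 = 24 per arm would be capped.

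Both options need the arm to be released during the procedure, by the independent clinician or by an equivalent such as a sealed envelope. That is the main practical cost beyond the wording.

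### Does writing the allocation in patient cards leave the clinical examiners' blinding unprotected?

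*Protocol*

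**What the plan says.** The opening blinding paragraph of the Protocol sets out who is blind. Patients are not told the material. Of the assessors it says: "Both the clinicians conducting the clinical and radiographic evaluations and the statistician analyzing the data will be blinded to the materials used". The exception is the operator: because the two materials are applied differently, "it is not possible for the clinician administering the treatment to be blinded".

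The next paragraph covers randomisation. An independent clinician allocates volunteers to two groups of 30 from a randomisation table, and "this information will be documented in patient cards". One endodontist performs all the treatments.

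The treatment procedure has the silicone bite impression disinfected and "stored under appropriate conditions in the patient's file to be used for subsequent radiographs". The follow-up text gives the schedule: "Follow-up visits at 1 week (for pain assessment only) and at 3, 6, and 12 months will be conducted". At these visits "necessary clinical examinations (percussion, palpation, presence-absence of sinus tract) will be performed", together with vitality testing and "radiographs taken using the silicone impression". The failure rule opens with "If issues such as pain, swelling, sinus tract formation, or lesion development are detected during follow-up". Radiographic evaluation is given to two endodontists from outside the trial, who read independently. The protocol does not say who performs the clinical examinations.

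**The concern.** The protocol promises blind evaluators and then, one paragraph later, chooses a patient-level record as the place for the allocation. Nowhere does it mention a code, sealed or separate storage, or a restriction on access. Patient records are in use at follow-up, since the impression kept in the patient's file is needed for the later radiographs. It is easy to picture an examiner with the card to hand.

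The clinical examination would be affected most. Swelling or a sinus tract found at 3, 6 or 12 months can make the case a failure, and the examiner is neither named nor said to be outside the trial. An examiner who knew the material could judge a doubtful sign differently in the two groups. That would bias the comparison of failures, and a larger sample would not remove the bias.

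**Working it through.** The protocol gives no figure to reproduce here, so the check is to set the relevant statements side by side and ask what must be true for blinding to fail.

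**Is there a contradiction?** The blinding paragraph says the evaluators are blind; the randomisation paragraph says the allocation goes on a card. Both can be true. The operator must know which material to place, cannot be blinded, and is not the person who randomises. The allocation therefore has to pass from the independent clinician to the operator through some record, and the card is one. The two statements would conflict only if the protocol also gave evaluators the card, and it does not.

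**What would unblinding require?**

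1. The card shows the material and not just a group label. The natural reading of the recording clause is the group assignment, but the protocol does not say in what form.
2. The clinical examiner sees the card. The protocol does not say so. The reuse of the silicone impression does not settle this: it would matter only if the card were kept in the same file and the examiner, not the operator or an assistant, took the impression out. Neither is stated.

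Both conditions must hold, and the second would itself depart from the blinding commitment.

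**Who could be affected?** Not the radiographic readers as described, since they come from outside the trial; that is a partial safeguard, though not an access rule. Not the patients, who are stated to be blind. The clinical examiners remain.

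**How far does it reach?** There are four scheduled follow-up visits (1 week, 3, 6 and 12 months). The 1-week visit is for pain only, so clinical examination applies at 4 − 1 = 3 visits. It is tempting to go further and count how many of the four named failure signs depend on the clinical examiner, but such a count is not sound. The list is introduced as examples, the protocol does not say who detects pain or swelling, and percussion and palpation findings might bear on the decision too. Any such fraction would be the reader's own partition.

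**Can bias be sized?** No. The protocol gives no failure rate, no rate of unblinding and no indication of how far knowledge of the material would shift a clinical finding. Sinus tract is recorded as present or absent, which leaves less to judgement than a graded score, but that does not make the effect zero.

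**The case for a change.** The strongest case for a change is this. How allocation is recorded and how blinding is kept are matters of trial conduct and belong in the protocol, so an unseen SAP does not excuse the silence. Nor is the protocol merely silent: it chose a patient-level record and attached no safeguard, just after promising blind evaluators. The radiographic readers are placed outside the trial, while the clinical examiners get no such separation and have only the general promise to rely on. A restricted log and coded cards would cost little and need no extra staff or visits.

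Much of this stands. The recording clause is as described, no code or access limit appears anywhere, and the examiners are not identified. The argument does not rest on the SAP, and neither does the answer to it.

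What does not follow is that the plan as fixed leads to a wrong or unreliable result. A commitment that the clinical evaluators are blind already obliges the team to keep the allocation from them; a code or an access rule is a means of meeting that obligation. Moving the allocation to a separate operator's treatment record would gain little on its face, because the protocol does not distinguish such a record from the patient card. The effective part would be the access limit, and the blinding statement already implies it.

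**Conclusion.** The concern does not hold as a fault in the plan. The protocol omits an operating detail, namely how the clinical examiners at 3, 6 and 12 months are kept from the card, but it states the outcome that the detail would serve, and nothing in it contradicts that outcome. A team following the text fills the gap in the ordinary way, by not showing the card to the examiners or by using a group code on what they see.

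The gap touches the clinical examinations at three of four follow-up visits and leaves the outside radiographic reading aside. No bias is shown, and none can be estimated from the document.

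This conclusion assumes that the blinding statement is carried out as written. Evidence that the clinical examiners work from cards naming the material would change it, but that would be a breach of the protocol's own rule and not a consequence of it.

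### Do the haemostasis steps contradict the 10-minute bleeding limit that takes a tooth off the study treatment?

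*Protocol*

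**What the plan says.** The protocol's account of the treatment procedure, common to both groups, sets out haemostasis in this order.

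- First step: "a moist cotton pellet soaked in NaOCl will be placed on the pulp wound surface for 2 minutes".
- Second step: "If bleeding continues, a new sterile cotton pellet soaked in 5.25% NaOCl solution will be placed for another 2 minutes".
- If bleeding still persists: "a second partial pulpotomy will be performed to reach non-inflamed pulp tissue, and the previous procedure will be repeated".
- Monitoring: "Bleeding will be checked every 2 minutes up to 10 minutes; if it stops at any of these intervals, pulp capping will be performed".
- Limit: "If bleeding continues for more than 10 minutes, the case will be deemed unsuitable for continuation with the current treatment". Total pulpotomy or root canal therapy is then considered.

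Two statements in the opening part of the protocol bear on how the rule is used. On allocation: "volunteers meeting the inclusion criteria will be randomized into two groups (n=30 each) by an independent clinician using a randomization table". This comes after the clinical examination and is described before the treatment procedure. On blinding: "it is not possible for the clinician administering the treatment to be blinded". The reason given is that the two materials are applied differently. A single endodontist performs all treatments.

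**The concern.** A reader who adds up the steps does not arrive at 10 minutes. Two pellets, a second cut and a repeat of the same two pellets make 8 minutes, and no further pellet is described for the last 2. If the second cut is taken as a new wound with a new clock, the total reaches 14 minutes. The threshold then seems to be 8, 10 or 14 minutes depending on who reads it.

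This would matter because the rule decides, after randomization, which teeth go on to receive the study material. The operator is not blinded, and the protocol does not say that the allocation is withheld until bleeding has stopped. A loose threshold could in principle let a tooth be kept in one arm when a similar tooth is dropped in the other. With 30 teeth per arm, each such tooth is 1/30 = 3.3% of its arm.

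**Working it through.** **Inputs, all from the haemostasis steps of the protocol**

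- First pellet: 2 minutes.
- Second pellet: 2 minutes.
- After the second cut: the procedure repeated, number of pellets not stated.
- Checks: every 2 minutes up to 10, so at 2, 4, 6, 8 and 10.
- Limit: bleeding for more than 10 minutes.

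The totals below count pellet time only, because the protocol gives no duration for the second cut.

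**The stated figure.** The limit is given twice, once as the end of the checks and once as the point beyond which the tooth is unsuitable. Both say 10 minutes, so the two sentences agree.

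**Literal repeat of two pellets**

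- First round: 2 + 2 = 4 minutes.
- First round plus repeat: 4 + 4 = 8 minutes.
- Left under the ceiling: 10 − 8 = 2 minutes, or one check interval.

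The 8 minutes is the length of the steps written out. It is not a threshold, because a tooth leaves the treatment only after more than 10 minutes. Nor is the interval from 8 to 10 left without a rule: the monitoring sentence provides for a check at 10 and for capping if bleeding has stopped.

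**Clock from the first pellet**

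- Before the second cut: 4 minutes.
- After it: 10 − 4 = 6 minutes, or 6 / 2 = 3 intervals.
- Total: 4 + 6 = 10 minutes.

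Three intervals exceed a two-pellet repeat. The text does not limit the repeat to two pellets, however, and the procedure can equally mean one cycle of applying a pellet for 2 minutes and checking. Read that way, the sequence fits 10 minutes exactly.

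**Clock restarted at the second cut**

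- Before the second cut: 4 minutes.
- After it: 10 minutes, or 10 / 2 = 5 intervals.
- Total: 4 + 10 = 14 minutes, or 14 / 2 = 7 intervals.

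**What remains open**

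| Reading | Total pellet time at the limit |
|---|---|
| Clock from first pellet | 10 minutes |
| Clock from second cut | 14 minutes |
| Difference | 14 − 10 = 4 minutes, or 4 / 2 = 2 intervals |

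A tooth that stops bleeding at 12 minutes in total is capped under the second reading and leaves the treatment under the first. A tooth that stops by 10 minutes is capped under both, and one still bleeding after 14 leaves under both.

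**Number of teeth affected.** The protocol gives no distribution of bleeding times. Supposing, purely for illustration, that 1 to 3 teeth per arm fell in the window, the share would be 1/30 = 3.3% to 3/30 = 10% of an arm. That is a restatement of the supposition and says nothing about the likely effect.

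**The case for a change.** The strongest case for a change is that this is an operative step in the protocol, not something usually left to an analysis plan. The decision follows allocation and rests with an operator who is not blinded. The second cut creates a fresh wound, so restarting the clock is a natural reading, and so is running it from the first pellet. Neither reading is a literal repeat of two pellets: one leaves three intervals after the cut and the other five. One sentence would settle it.

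Part of this stands. The start of the clock and the content of the repeat are not written down, and a reader wishing to replicate the procedure would have to ask.

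The step from there to a threat to the comparison does not stand. The rule is written once for both groups, whose procedures diverge only after haemostasis. A single operator applies it, so two operators cannot read it differently. The judgement most open to influence is whether bleeding has stopped at a given check. The same unblinded operator would make that call under a clock with a stated start, so anchoring the clock would not remove the discretion. Recording the time to haemostasis and the number of cuts would be informative, but the case form is not shown, and the absence of those fields from the protocol is not an error.

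**Conclusion.** The concern does not hold as a numerical contradiction. The protocol states one limit, 10 minutes, and states it consistently. Eight minutes is the sum of the steps spelled out, and it lies under a ceiling it was never meant to equal.

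What survives is a small ambiguity over the start of the clock: 10 or 14 minutes of total pellet time, a difference of two check intervals. It touches only teeth that stop bleeding between those two points, and their number cannot be derived from the document. No bias between the arms is shown or can be quantified.

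This conclusion assumes that the single operator settles on one reading and uses it for both groups, which the common wording supports. Under that assumption either reading gives a sound comparison. Which reading is clinically intended is for the sponsor's clinicians, and none is preferred here. The point is a gap in wording that the operator can fill sensibly, and it does not call for a change to the plan.

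### Does the lack of a named preoperative pain score weaken the comparison of first-week pain?

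*Protocol*

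**What the plan says.** The Protocol's follow-up paragraph says of the patients that "they will be asked to fill out the postoperative pain scale for the first week after treatment", and asks them to "note any medications and dosages used if applicable". The visit schedule comes next: "Follow-up visits at 1 week (for pain assessment only) and at 3, 6, and 12 months will be conducted".

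Three steps before or at the start of treatment bear on the point. The opening paragraphs state that "After the necessary clinical examination, volunteers meeting the inclusion criteria will be randomized", with 30 per group. The description of the common treatment procedure begins "Prior to treatment, a periapical radiograph of the relevant tooth will be taken for diagnostic purposes", together with photographs, and then states "Deep local anesthesia will be achieved using lidocaine with 1/80,000 epinephrine". None of these sentences names a pain score. The content of the examination is not listed, and neither are the inclusion criteria to which it refers.

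**The concern.** Pain has its own form and its own visit, yet only postoperative scoring is described. The radiographs, by contrast, have a carefully standardised pretreatment image against which later ones are read. A reader therefore asks where the matching pretreatment pain score is.

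The question is fair because a baseline measurement is a matter of data collection. An analysis plan can choose a model later, but it cannot recover a score that was not taken before anesthesia and treatment. If none is taken, first-week pain cannot be adjusted for pain on the same scale before treatment, and any chance difference between the arms in starting pain stays unseen. In a trial of 60 patients, that could mean a wider confidence interval than necessary.

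**Working it through.** **What the text establishes.** Scheduling a postoperative scale after treatment is correct for that instrument, and no other sentence conflicts with it. The Protocol does not announce an analysis of change from baseline, which would need a preoperative score. It does not say that no such score is taken, and the examination before randomization, whose content is open, is a natural place for one. The omission is therefore possible but not shown.

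**Bias.** Allocation is random, so starting pain has the same expected distribution in both arms. The absence of a baseline score introduces no bias into a comparison of first-week pain. Only precision can be affected.

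**Precision: inputs.** The Protocol gives 30 per arm, 60 in total. It gives no pain scale, standard deviation, method of comparison or correlation r between preoperative and first-week pain. A numeric scale, a comparison of means and the values of r are therefore assumptions. The Protocol states no figure on this point that could be reproduced.

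**Formula.** Adjusting for one baseline covariate multiplies the variance of the treatment difference by (1 − r²). Estimating the covariate's slope costs a factor of 1 + 1/(60 − 4) = 57/56. The equivalent unadjusted size per arm is 30 divided by the product. The interval-width ratio is the square root of the product, with t quantiles on 57 instead of 58 degrees of freedom.

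| Assumed r | (1 − r²) × 57/56 | Equivalent per arm | Interval width, adjusted ÷ unadjusted |
|---|---|---|---|
| 0 | 1.018 | 29.5 | 1.009 |
| 0.1 | 1.008 | 29.8 | 1.004 |
| 0.3 | 0.926 | 32.4 | 0.963 |
| 0.5 | 0.763 | 39.3 | 0.874 |

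Break-even is where (1 − r²) × 57/56 = 1, that is r = √(1/57) = 0.13. Below that, adjustment loses slightly.

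**Many zero scores.** Pain scores often pile up at zero, which weakens the observed correlation. To show this, correlated normal scores (standard deviation 3) were rounded and cut to a 0–10 integer scale. The shares of zeros are again assumptions.

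- Underlying r = 0.3, with 50% zeros both before and after treatment: observed r is 0.25, equivalent to 31.4 per arm.
- Underlying r = 0.3, with 70% zeros both before and after: observed r is 0.21, equivalent to 30.8 per arm.
- Underlying r = 0.3, with 90% pain-free before treatment and 50% or 70% zeros after: observed r is 0.17 or 0.16, equivalent to 30.3 to 30.4 per arm.
- Underlying r = 0.5, with 50% or 70% zeros both before and after: observed r is 0.43 or 0.38, equivalent to about 35 to 36 per arm.

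The result runs from a small loss, through nothing, to a modest gain, and nothing in the Protocol says where in that range this trial lies.

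**The case for a change.** The best case for raising the point is that the score is nearly free and cannot be recovered later. It would take one more row on an existing form, at a visit that takes place anyway. Using it as a covariate costs at most about 2% in variance, and at r = 0.5 the gain is worth about 9 patients per arm (39.3 − 30). Precision is also scarce. Assuming a two-sided 5% level and 80% power, the detectable difference with 30 per arm is (1.960 + 0.842) × √(2/30) = 0.72 standard deviations. The difference between the arms in mean baseline pain has a standard error of √(2/30) = 0.26 standard deviations, so chance alone allows about ±1.96 × 0.26 = ±0.51.

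Part of this stands. An uncollected score is lost for good, so the answer cannot be that the analysis plan will deal with it. The cost is indeed low. A patient count of that size, however, needs a correlation of 0.5 with no pile-up at zero, and the Protocol supports neither. Chance imbalance is not a further harm, because the unadjusted confidence interval already allows for it. Any gain would also be confined to first-week pain: the clinical and radiographic assessments at 3, 6 and 12 months, on which failure is judged, are not addressed by it. That collecting one more covariate is cheap does not make a plan without it wrong.

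**Conclusion.** The concern does not hold. The Protocol contains no wrong or contradictory statement here, and following it as written gives an unbiased randomized comparison of first-week pain with or without a preoperative score. Whether such a score is missing cannot be settled from the text, since the pretreatment examination is not itemised.

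If none is taken, the most that is forgone is precision on a measure that the Protocol does not rank. Adjustment would be equivalent to between 29.5 and 39.3 patients per arm, against the actual 30, for r from 0 to 0.5, and to about 31 per arm at an underlying r of 0.3 with half or more of the scores at zero. These figures rest on an assumed numeric scale, correlation, share of zeros and covariate-adjusted comparison of means, none of which the Protocol gives. Recording preoperative pain is a reasonable preference, but its absence from the text is not a defect.
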